		10.5.3	Impulsiv	e-Compulsive Disorders	41
		10.5.4	Ring Acc	ceptability	41

Statistical Analysis Plan	Version: 1.0	FERRIN	
Quinagolide	31MAY2022	PHARMACEUT	
FE 999051 trial 000165	CONFIDENTIAL	Page 4	

11	Interim Analyses	+ ∠
12	Deviations from Protocol Analysis	43

1 Introduction

This document describes the planned statistical analyses for trial 000165, and is based on versions 4.0, 5.0, and 6.0 of the clinical trial protocol dated 9th of July 2018, 27th of March 2019, and 29th of May 2020.

During this trial subjects were randomized under three consecutive versions of the protocol; version 4.0, version 5.0, and version 6.0. As the majority of subjects were randomized under protocol version 5.0, this will be used as the basis for the clinical trial report.

These protocol amendments included modifications to the eligibility criteria, modifications to the overall trial design, and changes to reflect the impact of the COVID-19 pandemic on the conduct of the trial. The change in trial design was in protocol version 6.0, the quinagolide extended-release vaginal rings were administered sequentially for 4 menstrual cycles instead of 8 menstrual cycles. Therefore, in version 6 subjects completed treatment Part A (cycles 1 to 4) only, there was no treatment Part B (cycles 5 to 8), and the follow-up period was for one menstrual cycle only (cycle 5).

The trial was terminated early. The decision was taken due to the results from the parallel phase 2 trial in Europe (Trial 000295) and the continued difficulties with subject recruitment.

Furthermore, due to the low number of subjects recruited, no interim analysis will be performed, and no statistical analysis will be performed. Instead results are presented as descriptive statistics by treatment group separately for Part A and Part B. In this SAP when results are summarized by treatment it means two tables one for Part A (with 4 treatments, Placebo and the 3 doses of quinagolide) and one for Part B (with 6 treatments, Placebo followed by each of the 3 doses of Quinagolide and continued use of each of the 3 doses of quinagolide).

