2.6 Exploratory Endpoint

Changes in endometriosis biomarkers such as serum levels of VEGF, placenta growth factor (PlGF), interleukin 6 (IL-6) and soluble fms-like tyrosine kinase 1 (sFlt-1) at cycles 4 and 8.

3 Trial design

This is a randomized, double-blind, placebo-controlled, phase 2 trial assessing the efficacy, safety and dose-response of quinagolide extended-release vaginal rings administered sequentially for 4 menstrual cycles in women with moderate to severe endometriosis-related pain. In this trial, a menstrual cycle is considered the period from day 7 of return of menses (RM+7) in a cycle until the following day 7 of return of menses in the next cycle. Visits on RM+7 can be scheduled on RM+6-10, i.e. day 6 to day 10 of return of menses.

The trial consists of the following periods:

- 1) Screening: starting immediately after the signing of the informed consent(s) and including a run-in period of two complete menstrual cycles (cycles -2 and -1)
- 2) Part A: double-blind, placebo-controlled treatment with three doses of quinagolide extended-release vaginal ring administered sequentially for four menstrual cycles (cycles 1, 2, 3 and 4)
- 3) Part B: double-blind, extension treatment with three doses of quinagolide extendedrelease vaginal ring administered sequentially for four menstrual cycles (cycles 5, 6, 7 and 8)
- 4) Follow-up: post-treatment follow-up period of two menstrual cycles (cycles 9 and 10)

Statistical Analysis Plan	Version: 1.0	FERRING
Quinagolide	31MAY2022	PHARMACEUTICALS
FE 999051 trial 000165	CONFIDENTIAL	Page 11 (44)

Abbreviations: B&B=Biberoglu and Behrman Scale, BTM=bone turnover markers, E2=estradiol, Echo=echocardiography, ECG=electrocardiography, EHP-30=Endometriosis Health Profile-30 Questionnaire, LH=luteinizing hormone, LH+7=7 days after LH surge, NRS=Numerical Rating Scale, P4=progesterone, PGIC=Patient Global Impression of Change, PGIS=Patient Global Impression of Severity, PG=pharmacogenetic(s), PK=pharmacokinetic(s), QICD=questionnaire for impulsive-compulsive disorders, QVR=quinagolide vaginal ring, RM=return of menses, RM+7=day 7 of return of menses, TVU=transvaginal ultrasound

- In case of technical issues at the start of the run-in period, subjects are allowed to re-start e-Diary recording for cycle -2. а

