7.3 Prior and Concomitant Medication

Prior and concomitant medication will be summarised by ATC classification 1st level (alphabetically), ATC classification 2nd level (in decreasing order of frequency) and treatment group. These medications will be tabulated separately for:

- 1) Prior medication; i.e. medication taken exclusively prior to treatment (i.e. with stop date before date of first ring insertion);
- 2) Concomitant medication, i.e. medication taken during the treatment period (i.e. medication that was not stopped before date of first ring insertion and not started after the last ring removal.
- 3) Post-treatment medications, i.e. medications starting after the treatment period (i.e. with start after the last IMP removal).

The number of subjects with "any medication" will be included in these tables. If the timing of the dose of a concomitant medication cannot be established in relation to the administration of IMP, it will be considered as concomitant medication.

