10.1 General Considerations

Safety parameters will be evaluated for the safety analysis data set.

All safety summaries will be performed by treatment:

For adverse events (AE) and concomitant medications the following rules will apply;

Treatment period	AE and concomitant medications to be included
Part A	Start after start of IMP, and start date before or equal to the date of the end-of-cycle 4 visit, if missing use date of premature discontinuation
Part B	Start date after the date of the end-of-cycle 4visit and before or equal to date last ring removal, if missing use date of premature discontinuation.

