10.2 Adverse Events

AEs are classified according to MedDRA version 20.0.

Written narratives will be issued for all serious AEs (including deaths) and AEs leading to withdrawal.

A pre-treatment adverse event is any adverse event occurring after signed informed consent and before start of IMP or a pre-existing condition that worsens in intensity after signed informed consent but before start of IMP. Pre-treatment AEs will be presented in a separate data listing only.

A treatment-emergent adverse event (TEAE) is any adverse event occurring after start of IMP and before the end-of-trial visit, or a pre-treatment adverse event or pre-existing medical condition that worsens in intensity after start of IMP and before the end-of-trial visit.

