10.2.2 Incidence of Adverse Events

Treatment-emergent adverse events will be summarised

The tables will display the total number of subjects reporting an AE, the percentage of subjects (%) with an AE, and the number of events (E) reported. AEs will be presented by SOC sorted alphabetically and PT sorted in decreasing frequency of occurrence.

Summary tables will be prepared for:

- All treatment emergent adverse events
- Treatment emergent adverse events with an incidence $\geq 5\%$ of subjects in any treatment group
- Treatment emergent related adverse events
- Treatment emergent related serious adverse events
- Treatment emergent non serious adverse events with an incidence ≥ 5% of subjects in any treatment group
- Treatment emergent unrelated adverse events
- Treatment emergent adverse events leading to death
- Treatment emergent adverse events leading to withdrawal
- Treatment emergent mild adverse events
- Treatment emergent moderate adverse events
- Treatment emergent severe adverse events
- Treatment emergent related mild adverse events
- Treatment emergent related moderate adverse events
- Treatment emergent related severe adverse events
- Treatment emergent serious adverse events

Supporting data listings will be provided for:

- All adverse events sorted by centre and subject no.
- All adverse events sorted by MedDRA Preferred Term
- Serious adverse events
- Adverse events leading to death
- Adverse events leading to withdrawal.

The listings will include information whether the AE occurred during the COVID-19 trial hold.

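### The SAP's adverse event tables close before the treatment-emergent period does, so treatment-emergent events that start in follow-up appear in no summary table

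*SAP*

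**What the plan says.** SAP 10.2 says a treatment-emergent adverse event (TEAE) "is any adverse event occurring after start of IMP and before the end-of-trial visit", or an earlier condition that worsens over the same period. Footnote g in protocol 9.8 (version 6.0) has the same definition, and protocol 9.8 plans to summarise these events.

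SAP 10.1 sets the date rule for entry to the tables and has two rows:

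- Part A takes events after start of treatment with "start date before or equal to the date of the end-of-cycle 4 visit, if missing use date of premature discontinuation".
- Part B takes events with "Start date after the date of the end-of-cycle 4visit and before or equal to date last ring removal", again falling back on premature discontinuation if that date is missing.

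SAP 10.1 also makes every safety summary a by-treatment summary. SAP 1 fixes what that means: "In this SAP when results are summarized by treatment it means two tables one for Part A" and one for Part B. No row or table covers follow-up, and no adverse event table pools the whole trial.

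Follow-up exists under every design described. SAP 3 gives two post-treatment cycles (9 and 10) after Part B. SAP 1 says version 6.0 has no Part B and one post-treatment cycle (5). Protocol 7.2.2.11 has adverse events recorded until the end-of-trial visit.

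**The concern.** Two adjacent SAP sections give different end dates for the same set of events. An event that starts in follow-up meets the definition in SAP 10.2 but neither date rule in SAP 10.1. The same cut-off carries into the overview table (SAP 10.2.1), the incidence tables (SAP 10.2.2), the dizziness, syncope and vaginal event tables (SAP 10.2.3) and the impulse-control adverse event table (SAP 10.5.3).

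This matters because SAP 1 and 9.3 drop all inferential analysis, which leaves the descriptive TEAE tables as the main summary of safety. A table presented as covering every TEAE would not do so. The serious-event table and the one titled "Treatment emergent adverse events leading to death" would have the same gap.

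It does not look like a deliberate choice. SAP 7.3 gives medications their own post-treatment table ("Post-treatment medications, i.e. medications starting after the treatment period"), so the period was considered there. SAP 12 lists the departures from the planned analysis and does not mention this one.

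**Working it through.** The plan states no figure on this point, so there is nothing to reproduce. The check applies the SAP 10.1 date rules and the SAP 10.2 definition to each possible onset day and counts the days that are treatment-emergent but in neither table.

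**Inputs**

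- Part A plus Part B design: 8 treatment cycles and 2 follow-up cycles (SAP 3).
- Version 6.0: 4 treatment cycles and 1 follow-up cycle (SAP 1).
- Cycle length L of 24 to 35 days. This is the run-in requirement in protocol 4.1.1 (inclusion criterion 11). That it holds after randomization is an assumption.
- Day 0 is the first ring insertion and onset days count from day 1. Visits fall exactly at cycle boundaries, so the RM+6-10 visit window is ignored.

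**Completer, Part A plus Part B.** The last ring is removed on day 8L and the end-of-trial visit is on day 10L. The definition says before that visit, so TEAE days run from 1 to 10L − 1. Days up to and including 8L are in a table. Days 8L + 1 to 10L − 1 are in none, which is 2L − 1 days.

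**Completer, version 6.0.** The last ring comes out at the end-of-cycle 4 visit, day 4L, so the Part B window is empty. The end-of-trial visit is on day 5L. TEAE days run from 1 to 5L − 1, and days 4L + 1 to 5L − 1 are in no table, which is L − 1 days.

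| Design | L | TEAE days | Days in no table | Share |
|---|---|---|---|---|
| Part A + B | 24 | 10×24 − 1 = 239 | 2×24 − 1 = 47 | 47/239 = 19.7% |
| Part A + B | 28 | 279 | 55 | 19.7% |
| Part A + B | 35 | 349 | 69 | 19.8% |
| Version 6.0 | 24 | 5×24 − 1 = 119 | 24 − 1 = 23 | 23/119 = 19.3% |
| Version 6.0 | 28 | 139 | 27 | 19.4% |
| Version 6.0 | 35 | 174 | 34 | 19.5% |

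**Early stopper.** Protocol 6.1.1 (version 6.0) puts the end-of-trial visit within 2 weeks of the end-of-treatment visit when the reason is an adverse event. If a woman stops in Part A on day D, has her end-of-treatment visit that day and her end-of-trial visit on day D + 14, then days D + 1 to D + 13 are in no table: 13 days. A later end-of-treatment visit lengthens the gap, and the 7-day target for that visit is only a preference, so the documents set no firm maximum. For other reasons the two visits can coincide; if they do so on the cut-off date, the gap is zero.

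**After the fix.** With a window running to the end-of-trial visit, no onset day in the TEAE period is left outside the tables.

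**The case against.** The strongest reply is that little is hidden, and much of it stands.

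- **Listings and narratives.** SAP 10.2.2 lists all adverse events, with separate listings for serious events, deaths and withdrawals. SAP 10.2 requires narratives for serious events, including deaths, and for events leading to withdrawal. A reader might infer that a death in follow-up would go unreported, or that protocol 8.5.1 on deaths within four weeks of treatment would be breached. Neither follows. That text concerns documenting and reporting the event, and only the table count is affected.
- **Valve findings.** A reader might infer that an echocardiogram done after the last ring removal is lost. SAP 10.5.2 tabulates clinically significant echocardiography findings by treatment, and the SAP 10.1 date rule covers only adverse events and concomitant medications. Only the related adverse event record would miss its table.
- **Withdrawals.** An event that causes a woman to stop treatment starts on or before the stop and falls inside the window. Only withdrawal from the trial during follow-up could be affected.
- **Size.** The 19% to 20% is a share of time and cannot be read as a share of events. The documents give no event rate for follow-up and do not say how many women reached it. Protocol 1.3 reports that most phase 1 events with a single ring began in the first week, which suggests a smaller share.
- **Protocol version.** SAP 1 makes version 5.0 the basis for the report, and only version 6.0 is available here. A departure from the version 5.0 tabulation plan cannot be shown.

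It could also be said that SAP 10.1 only allocates events to periods and excludes nothing. That does not help: an event allocated to neither period has no table to enter. The contradiction within the SAP also stands whichever protocol version applies.

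**Conclusion.** The concern holds as a fault in the summary tables. Followed as written, SAP 10.1 leaves out of every TEAE table the events that start after the Part A or Part B cut-off, although SAP 10.2 counts them as treatment-emergent and the trial collects them. The last-ring-removal cut-off belongs to the Part B row; Part A closes at the end-of-cycle 4 visit. For version 6.0 completers the two dates are the same, so cycle 5 is left out.

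The days left out for completers, 47 to 69 or 23 to 34, rest on cycles staying at 24 to 35 days and on visits falling at cycle boundaries. The number of events affected cannot be estimated from the documents. For early stoppers the gap varies and can be zero.

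The documents do not support a claim that safety events disappear from the report. They support a narrower one: table titles and counts would not match the SAP's own definition, in a report where those tables are the main safety summary, and the mismatch is undeclared. It should be corrected before the tables are produced.

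**What to change.** Add a third row to SAP 10.1, headed Follow-up, for adverse events that start after the applicable cut-off and before the end-of-trial visit. The cut-off is the last ring removal for women in Part B, the end-of-cycle 4 visit for those who complete Part A and do not start Part B, and premature discontinuation for early stoppers where the fallback applies. Tabulate these events by the treatment or sequence last received, separately from Part A and Part B, at least for all TEAEs, serious TEAEs and deaths. Extend the meaning of by-treatment in SAP 1 to match.

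If the sponsor prefers tables that end at the present cut-offs, retitle them as on-treatment events and declare the departure from the TEAE definition in SAP 12.

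The cost is SAP wording and a few extra tables; no new data are needed. The drawback is that follow-up events occur off the ring and are less specific to the drug, which is why they should be shown separately and not added to the Part A or Part B counts.

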10.2 Adverse Events

AEs are classified according to MedDRA version 20.0.

Written narratives will be issued for all serious AEs (including deaths) and AEs leading to withdrawal.

A pre-treatment adverse event is any adverse event occurring after signed informed consent and before start of IMP or a pre-existing condition that worsens in intensity after signed informed consent but before start of IMP. Pre-treatment AEs will be presented in a separate data listing only.

A treatment-emergent adverse event (TEAE) is any adverse event occurring after start of IMP and before the end-of-trial visit, or a pre-treatment adverse event or pre-existing medical condition that worsens in intensity after start of IMP and before the end-of-trial visit.

10.2.1 Overview of Treatment-Emergent Adverse Events

An AE overview summary table will be prepared including the number of subjects reporting an AE, the percentage of subjects (%) with an AE, and the number of events (E) reported, for the following categories:

• All TEAEs

- TEAEs leading to Deaths
- Serious TEAEs
- TEAEs leading to withdrawal
- Adverse drug reactions (as assessed by investigator)
- Serious Adverse drug reactions

10.2.2 Incidence of Adverse Events

Treatment-emergent adverse events will be summarised

The tables will display the total number of subjects reporting an AE, the percentage of subjects (%) with an AE, and the number of events (E) reported. AEs will be presented by SOC sorted alphabetically and PT sorted in decreasing frequency of occurrence.

Summary tables will be prepared for:

- All treatment emergent adverse events
- Treatment emergent adverse events with an incidence $\geq 5\%$ of subjects in any treatment group
- Treatment emergent related adverse events
- Treatment emergent related serious adverse events
- Treatment emergent non serious adverse events with an incidence ≥ 5% of subjects in any treatment group
- Treatment emergent unrelated adverse events
- Treatment emergent adverse events leading to death
- Treatment emergent adverse events leading to withdrawal
- Treatment emergent mild adverse events
- Treatment emergent moderate adverse events
- Treatment emergent severe adverse events
- Treatment emergent related mild adverse events
- Treatment emergent related moderate adverse events
- Treatment emergent related severe adverse events
- Treatment emergent serious adverse events

Supporting data listings will be provided for:

- All adverse events sorted by centre and subject no.
- All adverse events sorted by MedDRA Preferred Term
- Serious adverse events
- Adverse events leading to death
- Adverse events leading to withdrawal.

The listings will include information whether the AE occurred during the COVID-19 trial hold.

10.2.3 Incidence of Adverse Events of Special Interest

10.2.3.1 Dizziness/Pre-syncope

Treatment-emergent adverse events of dizziness/pre-syncope will be summarised, similar to the tables described in 10.2.2. Two tables will be prepared one with all TEAE and one with related TEAE(as assessed by the investigator). An AE is considered to be dizziness/pre-syncope if the PT is included in the list below:

Dizziness Dizziness postural Dizziness exertional Persistent postural-perceptual dizziness Procedural dizziness Pre-syncope Vertigo Vertigo positional Vertigo CNS origin

10.2.3.2 Dysmenorrhea, Abdominal Pain, Pelvic Pain, Lower Back Pain and Dyspareunia

Dysmenorrhea, Abdominal Pain, Pelvic Pain, Lower Back Pain and Dyspareunia is reported as part of the efficacy reporting.

10.2.3.3 Vaginal bleeding

Vaginal bleeding is reported as part of the efficacy reporting

10.2.3.4 Syncope

Treatment-emergent adverse events of syncope will be summarised, similar to the tables described in 10.2.2. Two tables will be prepared one with all TEAE and one with related TEAE (as assessed by the investigator). An AE is considered to be syncope if the PT is included in the list below:

Syncope Loss of consciousness Altered state of consciousness

10.2.3.5 Vaginal Irritation and/or Vaginal Infection

Treatment-emergent adverse events of Vaginal Irritation and/or Vaginal Infection will be summarised, similar to the tables described in 10.2.2. Two tables will be prepared one with all TEAE and one with related TEAE(as assessed by the investigator). An AE is considered to be Vaginal Irritation and/or Vaginal Infection if the High level term is included in the list below:

vulvovaginal signs and symptoms vaginal and vulval infections and inflammation

10.3 Safety Laboratory Variables

Baseline for all laboratory analyses will be the values obtained at the last assessment prior to the first dose of the investigational medicinal product (IMP). Treatment-emergent laboratory data will include tests completed after the first dose of IMP through the residual time of drug effect. End of trial will include the last post-baseline observation during the trial. Safety lab values are planned to be measured four times, at baseline, at end of part A, at end of party B, and at end of trial. In case of premature discontinuation an extra measurements is planned. If premature discontinuation is during part A the extra measurement will be used both as end of part A and end of trial measurement, if premature discontinuation is during part B the extra measurement is used as both end of part B and end of trial measurement

Laboratory variables will be grouped under "Haematology", "Clinical Chemistry" or "Urinalysis"

10.3.1 Summary Statistics

Mean change and mean percentage (%) change from baseline at end of trial will be presented for each laboratory variable. In addition, descriptive statistics, i.e., the number of subjects with data, mean (standard deviation), median, minimum, and maximum values, will be presented for observed values and change from baseline at each time-point for each laboratory variable.

10.3.2 Laboratory Variable Changes Relative to Normal Range

As the trial has been prematurely discontinued, it has been decided, due to the low number of subjects, that no shift tables will be prepared. Clinical significant changes in laboratory values are presented in the AE tables.

10.3.3 Data Listings

Data listings will be prepared by treatment for all subjects with any abnormal laboratory value at any time-point (including screening, baseline).

10.3.4 Urinalysis

Incidence of changes in urinalysis will be summarised. Summary tables with number of subjects with change from *Absent* at baseline to *Present* during trial will be summarised.

10.4 Vital Signs and ECG

10.4.1 Vital Signs

Baseline for all vital signs analyses will be the values obtained at the last assessment prior to the first dose of IMP. Treatment-emergent vital signs data will include tests completed after the first dose of IMP through the time of residual drug effect. End of trial will include the last post-baseline observation during the trial.

